13.1.4.2 Clinical Laboratory Evaluations

Descriptive summaries (mean, SD, median, minimum, and maximum) of actual (absolute) values and changes from baseline values will be presented for clinical laboratory values by treatment group at each time point.

The number of participants with clinical laboratory values categorized as below, within, or above normal ranges will be tabulated showing change from baseline (shift tables) for each clinical laboratory analyte by treatment group and by study visit.

Laboratory values that are outside the normal range will also be flagged in the data listings and presented with the corresponding normal ranges. Any out-of-range values that are identified by the investigator as being clinically significant will also be shown in a data listing.

13.1.4.3 Vital Signs

Descriptive summaries (mean, SD, median, minimum, and maximum) of actual values and changes from baseline will be calculated for systolic blood pressure, diastolic blood pressure, heart rate, and respiratory rate, by treatment group.

13.1.4.4 Twelve-lead Electrocardiograms

The number and percentage of participants with normal and abnormal ECG findings will be summarized by treatment group at each time point. Abnormal results will be grouped as clinically significant and not clinically significant.

Descriptive summaries (mean, SD, median, minimum, and maximum) will be presented for ECG measures of PR interval, QRS interval, QT interval, QTc interval (Bazett's and Fridericia's correction methods), and heart rate by treatment group at each time point.

13.1.4.5 Local Site Irritation

Change in local irritation scores (for erythema and edema, see [Table 10-1](#)) from baseline to Day 57 will be calculated. Descriptive summaries (mean, SD, median, minimum, and maximum) will be provided for absolute values and for change from baseline by treatment group. In addition, number and percentages of participants with each score will be summarized categorically for erythema and edema separately.

13.1.4.6 Physical Examination Findings

The number and percentage of participants with normal and abnormal findings in the complete physical examination will be displayed by treatment group.

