2.2. Schedule of Events

Table 2-1: Schedule of Events

Day(s)	Screening	Administration Period														ET	FU		
		1-2 ^a				4 ^b	7 ^{a,b}	10 ^b	18 ^b	28 ^b	42 ^b	56-57 ^a							
Window	-	-				±1	±1	±1	±1	±1	±1	±1				-	±1		
Time from Admin. (hr.)		Pre-dose	0	4	10	24 ^c						Pre-dose	0	4	10	24 ^c			
Informed consent	X																		
Inclusion/Exclusion	X																		
Medical history	X																		
Concomitant medications	X	X					X	X	X	X	X	X					X	X	X
Physical exam ^d	X	X	X	X	X	X	X	X	X	X	X	X	X	X	X	X	X	X	X
Vaginal speculum exam ^e	X	X				X		X		X	X	X					X	X	X
Mammogram ^f	X																		
Cervical screening test ^g	X																		
Height and weight	X																		
Vital signs ^h	X	X		X	X	X		X		X	X	X		X	X	X	X	X	X
12-Lead ECG ⁱ	X	X		X				X		X	X		X		X		X	X	X
Serum biochemistry	X	X						X		X	X						X	X	X
Hematology	X	X						X		X	X						X	X	X
Urinalysis	X	X						X		X	X						X	X	X
Coagulation panel	X	X						X		X	X						X		X
TSH	X																		
FSH ^j	X																		
Drugs of abuse ^k	X																		
Viral serology ^l	X																		
Vaginal pH ^m	X	X							X	X	X						X	X	X
Vaginal cytology	X	X							X	X	X						X	X	X
Transvaginal ultrasound	X ⁿ																X	X	
Assessment of VVA symptoms ^o	X								X	X	X	X						X	X
Diary administration and review ^p	X	X					X	X	X	X	X	X						X	
Study drug administration ^q			X			X	X	X	X	X	X		X						
MENQOL		X															X	X	
Usability and Acceptability questionnaire						X					X						X	X	
PK blood samples ^r		X	0.5, 1, 2, 4, 5, 8, 12 (hr.)		X	X	X	X	X	X	X	X	0.5, 1, 2, 4, 5, 8, 12 (hr.)	X					X
AE ^s		X	X	X	X	X	X	X	X	X	X	X	X	X	X	X	X	X	X

Abbreviations: AE = adverse event; ECG = electrocardiogram; ET = early termination; FSH = follicle-stimulating hormone; FU = follow-up; HBsAg = hepatitis B surface antigen; HCV = hepatitis C virus; HIV = human immunodeficiency virus; hr. = hour; IP = investigational product; MENQOL = Menopause-specific Quality of Life; PK = pharmacokinetics; TSH = thyroid-stimulating hormone; VVA = vulvar vaginal atrophy

- a. Multiple non-PK assessments scheduled for the same time point should be performed on the same day as dosing. PK blood sample procedures should follow the defined window, if applicable.
- b. Samples for PK trough levels should be obtained prior to DARE-VVA1 insertion on Days 4, 7, 10, 18, 28, and 42. Administration of DARE-VVA1 will take place at site on the day of these visits, after collecting the trough PK sample.

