- c. Participants will be discharged from the site after all 24-hour assessments have been completed. Day 1-2 only: Administration of DARE-VVA1 should be the final activity before discharge, following completion of all 24-hour assessments.
- d. A complete physical examination (excluding rectal examinations) will be performed at screening and will include a manual breast examination. Subsequent physical examinations will be abbreviated and will be directed based on signs and symptoms exhibited by the participant.
- e. Vaginal speculum examinations will include assessment of local irritation (scoring of erythema and edema), and a full pelvic examination.
- f. Mammograms should be conducted ONLY in those participants who have not had one within the last 2 years.
- g. Cervical screen testing should be conducted ONLY in those participants who have a cervix and have not had cervical screening within the last 5 years.
- h. Vital signs assessments will include pulse rate, respiratory rate, and supine blood pressure. Assessments will be performed after the participant has been in a supine position for at least 5 minutes. Temperature will also be measured.
- i. 12-lead ECGs will be performed after the participant has been supine for at least 5 minutes.
- j. FSH will be assessed in all hysterectomized women who have not undergone bilateral oophorectomy, and in non-hysterectomized women who have not undergone bilateral oophorectomy and have experienced spontaneous amenorrhea for ≥ 6 months but < 12 months, to confirm postmenopausal status.
- k. Drugs of abuse will be measured at screening by local laboratories via urinalysis and alcohol screens versus a commercially available urine dipstick.
- l. Viral serology: a blood sample will be collected for the determination of HIV, HCV, and HBsAg.
- m. Vaginal pH will be evaluated using commercially available pH strips.
- n. Transvaginal ultrasound will be performed on women who have not undergone a hysterectomy. During screening, the pelvic examination, with assessment of local irritation and cervical screening (if needed), should be performed prior to the transvaginal ultrasound.
- o. Participants will be required to engage in vaginal intercourse or other sexual activity (masturbation, etc.) at least 1 time between Days 49-56, and complete an assessment of VVA symptoms in their diary.

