6.4. Objectives and Endpoints

Objectives	Endpoints
Primary	

 • To evaluate the safety and tolerability of DARE-VVA1 by intravaginal administration 	
 • Adverse events • Clinical laboratory findings • Vital signs results • 12-lead ECG results • Physical examination findings • Change in local site irritation scores from baseline to Day 57 • Endometrial thickness (measured by transvaginal ultrasound) in women who have not undergone hysterectomy prior to the study

 • To determine the plasma PK of DARE-VVA1 after intravaginal application 	
 • Standard PK parameters from noncompartmental analysis on Day 1, with steady-state parameters on Day 56 • Dose-proportionality of tamoxifen

Secondary	

 To evaluate preliminary efficacy and pharmacodynamics of DARE-VVA1 in terms of most bothersome symptom, dyspareunia, and changes in vaginal cytology and pH 	
 Change of vaginal pH from baseline to Day 57 Change in vaginal cytology (maturation index; percentage of basal and superficial cells) from baseline to Day 57 Change in most bothersome symptom from baseline to Day 56 Change in severity of dyspareunia from baseline to Day 56 Correlation between exposure and local changes
Exploratory	

 To evaluate the impact of DARE-VVA1 on quality of life using a menopause-specific instrument To assess the usability and acceptability of DARE-VVA1 	
 Change in the MENQOL questionnaire from baseline to Day 57 Responses to the Usability and Acceptability questionnaire over time

[figure not shown]

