10.2. Study Periods and Visits

10.2.1 Screening

The participant must be screened within 21 days before enrollment in the study. Assessments to be conducted during screening are shown in the schedule of events (Table 2-1). No study-specific assessments should be conducted until the participant has provided written informed consent (see Section 14.4.1).

Participants who have not had mammograms and CSTs in the timeframe indicated by the inclusion criteria will undergo these assessments during screening.

Procedures for rescreening participants who initially fail to meet study entry criteria are described in Section 14.3.

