10.3.1.2.3 Physical Examination

A complete physical examination (excluding rectal examinations) will be performed at screening and will include a manual breast examination. Subsequent physical examinations, as indicated in the schedule of events ([Table 2-1](#)), will be abbreviated and will be directed based on signs and symptoms exhibited by the participant.

Clinically significant abnormal physical examination findings will be reported as an AE (see [Section 11.2](#)).

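### The by-arm physical examination table in 13.1.4.6 uses only the complete examination, which is done at screening, so the table for this primary safety endpoint holds no post-dose observations

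*Combined protocol and SAP*

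**What the plan says.** Protocol Section 6.4 lists "Physical examination findings" among the endpoints for the primary objective of safety and tolerability. Section 13.1.4.6 gives that endpoint one sentence of analysis: "The number and percentage of participants with normal and abnormal findings in the complete physical examination will be displayed by treatment group." It names no visit or time point.

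Section 10.3.1.2.3 defines the examinations. On the first: "A complete physical examination (excluding rectal examinations) will be performed at screening and will include a manual breast examination." Later examinations "will be abbreviated and will be directed based on signs and symptoms exhibited by the participant". Footnote d of Table 2-1 agrees: "Subsequent physical examinations will be abbreviated and will be directed based on signs and symptoms exhibited by the participant." The "Physical exam" row of that table is marked at screening and then before dosing on Day 1, through the treatment visits, at early termination and at follow-up. On timing, Section 10.2.1 says: "The participant must be screened within 21 days before enrollment in the study."

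Two general statements also bear on this. Section 13.1.4 names physical examination results as a safety variable and promises frequency counts for qualitative safety data. The synopsis uses the Safety population to summarize examination findings. Neither limits the summary to the complete examination, and neither assigns a table to the abbreviated ones.

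**The concern.** The subsection sits under Safety and Tolerability Analyses, and its table is laid out by treatment group, as a comparison of arms after exposure would be. The examination it selects takes place before any insert is given, so differences between arms in that table cannot reflect treatment or dose.

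At stake is whether a named primary safety endpoint, for a product not previously given to humans (5.3), has its own post-dose summary. A programmer who follows 13.1.4.6 literally would produce a baseline table under a safety heading, and the abbreviated examinations would have no table.

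**Working it through.** No plan figure needs reproducing and no power or error-rate calculation applies. The check sets the sections side by side.

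**Step 1: which examination feeds the table.** Section 13.1.4.6 specifies the complete examination.

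**Step 2: when that examination occurs.** Section 10.3.1.2.3, footnote d and the synopsis all place it at screening, and Section 10.2.1 puts screening before enrollment. That is one complete examination per woman, before dosing.

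**Step 3: what remains after dosing.** Every later mark on the Table 2-1 row is an abbreviated examination under footnote d. Post-dose complete examinations per woman: 0. Post-dose observations in the 13.1.4.6 table: 0 in each arm of 8, and 0 across the 40 planned women.

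**Step 4: whether a baseline table was intended.** Baseline characteristics have their own section, 13.1.2.3, which covers medical history, speculum examinations, mammograms and cervical screening tests. The physical examination is not there. Section 11.2 treats a condition present at screening as baseline, not as an adverse event, unless it deteriorates. So 13.1.4.6 is placed as a safety analysis but draws on data that the protocol elsewhere treats as baseline.

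**Step 5: comparison with the other primary safety endpoints.** Section 6.4 lists seven. Six have a post-dose summary in their own subsection:

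- Adverse events (13.1.4.1): treatment-emergent events by arm.
- Clinical laboratory (13.1.4.2): change from baseline and shift tables.
- Vital signs (13.1.4.3): change from baseline.
- ECG (13.1.4.4): normal and abnormal counts over the scheduled time points, with abnormal results split by clinical significance.
- Local irritation (13.1.4.5): change to Day 57 and counts per score.
- Endometrial thickness (13.1.4.7): change from baseline.

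The seventh, physical examination findings (13.1.4.6), has none.

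**Step 6: where post-dose findings go instead.** Section 10.3.1.2.3 says: "Clinically significant abnormal physical examination findings will be reported as an AE." Section 8.4 does the same for new clinically relevant findings after enrollment, and 11.2.1 for clinically relevant observations at a visit. Treatment-emergent events are tabulated by arm, with severity and relationship (13.1.4.1). The synopsis promises listings of all CRF data. What remains without a specified by-arm summary is mainly abnormal findings judged not clinically significant and not otherwise reported as adverse events.

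**The case against.** The strongest reply is that little of clinical importance depends on this table. Step 6 shows that findings that matter reach the by-arm adverse event tables. For an intravaginal product the key examination is the speculum examination, whose irritation scores have their own analysis in 13.1.4.5. This stands, and it limits the consequence.

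A second reply is that Section 13 is only a summary, that 13.1.4 already promises frequency counts for examination results, and that the SAP due before database lock can supply the table. It can; no SAP text is in the document supplied, so what it will say is unknown. But 13.1.4.6 states a rule and defers nothing, while 13.1.5, 13.1.6.2 and 13.1.6.3 explicitly leave items to the SAP. The broader wording in 13.1.4 does not change what the specific subsection says. The mismatch is itself a reason to correct it.

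A third reply is that symptom-directed examinations do not suit a table of normal and abnormal results. What is examined varies by woman and visit, so a normal rate has no common denominator. The ECG comparison is weaker for that reason, since ECGs are standardized. This stands and should shape the replacement table. It does not justify filling a safety table with screening data.

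A reader might go further and infer that post-dose examination findings are lost, or measure the loss by counting the later marks on the schedule. The documents do not support this. The adverse event and listing routes remain, and a scheduled symptom-directed examination is not a lost finding.

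**Conclusion.** The point holds. As written, the by-arm table for a listed primary safety endpoint contains no post-dose observations. This is a stated rule that misses its purpose, and it should be corrected.

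Its size is modest: the endpoint's own post-dose summary is missing, mainly for abnormal findings judged not clinically significant. The documents give no rate for such findings, so no number can be put on them. The conclusion assumes that *complete* in 13.1.4.6 has the same meaning as in 10.3.1.2.3 and footnote d, and that the SAP does not depart from 13.1.4.6.

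A reader might also infer that entry criteria will make the table look almost entirely normal and so falsely reassuring. The documents do not support that. Among examination findings, the inclusion criteria require normality of the vulva and vagina (apart from atrophic change), the cuff or cervix, and the breast. For general disease, exclusion 1 bars only significant conditions that would prevent compliance. A normal general examination is not required.

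**What to change.** Reword 13.1.4.6 and carry the wording into the SAP before database lock:

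- Report the complete screening examination as a baseline characteristic under 13.1.2.3.
- For the endpoint, show by arm the n (%) of women with any new or worsened abnormal finding at any abbreviated examination after the first dose.
- Define new or worsened against the pre-dose examinations (screening and Day 1 pre-dose), and note that an abbreviated examination is not like for like with the complete one.
- Split by clinical significance where the eCRF records it. Section 10.3.1.2.3 does not say that it does, so check this first.
- Count women with a finding, and do not present a normal rate by visit, because the later examinations are symptom-directed.

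The cost is one reworded sentence and one descriptive table, with no new procedure. If the change is made as a protocol amendment, it alters neither participant risk nor objectives, which are triggers for prior ethics approval under 14.8. Section 15.3.2 nevertheless sends amendments to the ethics committee unless they are logistical or administrative, so the sponsor should confirm how this one is classed.

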13.1.4.7 Endometrial Thickening

Change in endometrial thickness from baseline in women who have not undergone hysterectomy will be summarized descriptively by treatment group.

13.1.4.8 Prior and Concomitant Medications

Prior medications will be presented separately from concomitant medications. Medications that started before the first dose of IP will be considered prior medications whether or not they were stopped before the first dose of IP. Any medications continuing or starting after the first dose of IP will be considered to be concomitant. If a medication starts before the first dose of IP and continues after the first dose of IP it will be considered both prior and concomitant.

Summary tables by treatment group will be presented by World Health Organization-Anatomical Therapeutic Chemical Classification System (WHO-ATC) therapeutic category and preferred term for participants in the Safety population.

13.1.5 Pharmacokinetics

For noncompartmental analysis, plasma concentrations will be listed and summarized at each time point using descriptive statistics; geometric means and % coefficient of variation (%CV) will also be presented for the PK parameters by treatment group.

[Table 10-2](#) lists the PK parameters that are collected for each participant. The PK parameters will be summarized by dose using descriptive statistics. Calculation of PK parameters will be outlined in the SAP.

For the assessment of dose proportionality, the power model will be implemented for C_{max} and AUC_{0-t} .

13.1.6 Pharmacodynamics and Efficacy Analysis

Efficacy variables will be summarized and analyzed using the ITT population, unless otherwise specified.

13.1.6.1 Primary Analysis

There is no primary efficacy analysis planned for this study.

13.1.6.2 Secondary Analyses

The secondary efficacy endpoints are the following:

- Change of vaginal pH from baseline to Day 57
- Change in vaginal cytology (maturation index; percentage of basal and superficial cells) from baseline to Day 57
- Change in most bothersome symptom from baseline to Day 56
- Change in severity of dyspareunia from baseline to Day 56
- Correlation between exposure and local changes

Descriptive summaries (mean, SD, median, minimum, and maximum) involving change of vaginal pH and vaginal cytology will be presented by treatment group at each time point. In addition, an ANCOVA model will be used to assess treatment differences in change from baseline for vaginal pH, vaginal cytology, dyspareunia, and most bothersome symptom, using baseline score as a covariate. The *P* values will be informational, and no formal testing is planned for this study.

The change in severity from baseline for the most bothersome symptom identified by participants at screening will be summarized categorically by treatment group (see Section 10.3.3.3 for assessment details). In addition, the change in severity from baseline will also be summarized descriptively for each of the 5 symptoms evaluated at each time point.

For assessments of dyspareunia, change in severity from baseline will be summarized descriptively by time point and by treatment group. A categorical summary of severity will be presented by treatment group at each time point.

Pharmacodynamics will be assessed by correlating the dose administered to exposure of tamoxifen in plasma, and then by relating the exposure to local vaginal change in cytology and pH as well as to the reported symptomatology over 56 days. Additional details of this analysis will be provided in the SAP.

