STATISTICAL METHODS	
General:
 
For the purpose of all safety, efficacy, and other analyses where applicable, baseline is defined as the last measurement before the start of study drug administration.
 
Continuous endpoints will be summarized with number (n), mean, standard deviation, median, minimum, and maximum. In addition, change from baseline values will be calculated at each time point and summarized descriptively. For categorical endpoints, descriptive summaries will include counts and percentages.
 
Analysis Populations:
 
The ITT population, defined as all randomized participants, will be used to summarize participant disposition, demographics and baseline characteristic summaries, efficacy endpoints, and exploratory endpoints.
 
Efficacy evaluations include changes in vaginal pH, changes in vaginal cytology (maturation index; percentage of basal and superficial cells), change in dyspareunia, and change in most bothersome symptom. These will be summarized using the ITT population. For the analysis the exploratory endpoints, results from the MENQOL questionnaire and the Usability and Acceptability questionnaire will be summarized over time from baseline in the ITT population.
 
An analysis of covariance (ANCOVA) model will be used to assess treatment differences in change from baseline for vaginal pH, vaginal cytology, and most bothersome symptom, using baseline score as a covariate. With no formal testing planned for this study, the P values will be informational.
 
The Safety population, defined all participants who are enrolled and receive any amount of planned IP, will summarize the recorded AEs, clinical laboratory safety tests, vital signs, ECG results, physical examination findings, and any other parameter relevant for safety assessment.

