7. STUDY DESIGN

7.1. Overall Study Design and Plan

This is a Phase 1/2, randomized, multi-center, double-blind, parallel-arm, placebo-controlled, dose-ranging study to evaluate the safety, tolerability, PK, and PD of DARE-VVA1, a novel intravaginal tamoxifen product. The investigational product (IP) will be evaluated at 4 dose levels (1 mg, 5 mg, 10 mg, and 20 mg) and compared to a placebo vaginal insert. With each dose level, the IP will be administered intravaginally for 56 days, according to the following treatment schedule: once daily for 2 weeks then twice a week for 6 weeks.

Approximately 40 postmenopausal women, 20 who have undergone hysterectomy and 20 who have not, with VVA will be enrolled. After signing informed consent, eligible participants will be randomly allocated as follows: the 20 hysterectomized women will be allocated to 1 of the 5 treatment groups, and the 20 non-hysterectomized women will be randomly allocated to one of the same 5 treatment groups, such that each treatment group ends up with 4 hysterectomized women and 4 non-hysterectomized women, for a total of 8 women. (Figure 7-1).

Figure 7-1: Study Design

Abbreviations: D = day; FU = follow-up; N = number of participants

Participants must be healthy postmenopausal women aged 40 to 75 years (inclusive) and have moderate to severe VVA, as determined by a vaginal pH greater than 5 at the Screening Visit, $\leq 5\%$ superficial cells on vaginal cytology, and either at least 1 moderate or severe symptom on self-assessment of i) vaginal dryness, ii) vaginal and/or vulvar irritation/itching, iii) dysuria, or iv) vaginal pain with sexual activity (dyspareunia), or the presence of vaginal bleeding associated with sexual activity. Participants are required to have a normal-appearing vagina upon speculum examination. Participants with a cervix are required to have a normal appearing cervix upon speculum examination. Participants who have not undergone hysterectomy are required to have an endometrial thickness ≤ 4 mm. All participants are required to have a recent normal mammogram and manual breast examination at screening. Mammograms and CSTs will be conducted for those

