8.5. Participant Discontinuation/Withdrawal from the Study

Participants are free to discontinue the study at any time, for any reason, and without prejudice to further treatment. The investigator may remove a participant if, in the investigator's judgment,

continued participation would pose an unacceptable risk to the participant or to the integrity of the study data. All procedures for early termination must be completed. Reasons for removal or withdrawal may include:

- Withdrawal of consent
- Administrative decision by the investigator or sponsor
- Ineligibility
- Significant protocol deviation
- Participant noncompliance
- Safety concern by the investigator or sponsor
- Lost to follow-up

Participants who are withdrawn prior to completing all study visits may be replaced.

In the event of a participant's withdrawal, the investigator will promptly notify the sponsor and medical monitor and will make every effort to complete the Early Termination Visit assessments (Section 10.2.3). All withdrawn participants with ongoing clinically significant clinical or laboratory findings will be followed until the finding is resolved or medically stable; reasonable attempts will be made to follow-up with participants.

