9.5. Method of Assigning Participants to Treatment Groups

In this parallel-group randomized study, participants who meet study entry criteria will be randomly assigned in a 1:1:1:1:1 ratio, by history of hysterectomy, to 1 of the 5 treatment groups indicated in [Table 9-1](#). The randomization schedule will be computer-generated using a permuted block algorithm and will randomly allocate IP to randomization numbers. Study center will not be a blocking factor in the randomization schedule. The randomization numbers will be assigned sequentially by a member of the ICON Clinical Research Team who is not otherwise involved in the study. Contact details for obtaining randomization numbers are provided in the Study Reference Manual. The randomization schedule will be prepared by ICON Clinical Research before the start of the study. No one involved in the study performance will have access to the randomization schedule before official unblinding of treatment assignment. No participant will be randomized into this study more than once.

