10.3.3.3 Symptoms of Vulvar Vaginal Atrophy

At the Screening Visit, participants will rate the first 4 items in the list of VVA symptoms in [Table 10-3](#) as either not present (none), mild, moderate, or severe, and will indicate whether vaginal bleeding associated with vaginal activity is present or absent. They will then select 1 of the 5 symptoms as their most bothersome symptom. All 5 symptoms will be evaluated again during later study visits (see [Table 2-1](#)), and the change in severity from baseline will be determined. Changes from baseline in each participant's most bothersome symptom, as well as changes in dyspareunia (whether dyspareunia was the participant's most bothersome symptom or not), will be evaluated as study endpoints.

Symptoms to be evaluated are shown in [Table 10-3](#).

All participants will be required to engage in vaginal intercourse or other sexual activity (masturbation, etc.) at least 1 time between Days 49-56, and complete an assessment of VVA symptoms in their diary.

Table 10-3: Assessment of Most Bothersome Symptom

Symptom	Assessment
Vaginal dryness	None, mild, moderate, or severe
Vaginal and/or vulvar irritation/itching	None, mild, moderate, or severe
Dysuria	None, mild, moderate, or severe
Vaginal pain associated with sexual activity (dyspareunia)	None, mild, moderate, or severe
Vaginal bleeding associated with sexual activity	Presence versus absence

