13. STATISTICS

13.1. Statistical Analysis

This section presents a summary of the planned statistical analyses. An SAP that describes the details of the analyses to be conducted will be written prior to database lock.

An analysis of covariance (ANCOVA) model will be used to assess treatment differences in change from baseline for vaginal pH, vaginal cytology, dyspareunia, and most bothersome symptom, using baseline score as a covariate. With no formal testing planned for this study, the *P* values will be informational.

Summary statistics will be provided for the variables described below. For continuous variables, these statistics will typically include the number of participants, mean, standard deviation (SD), median, minimum, and maximum. For categorical variables, these statistics will typically include the number and percentage of participants in each category. The denominator for percentage will be based on the number of participants appropriate for the purpose of analysis.

For all calculations of change from baseline, the last observation recorded before the first administration of the insert (DARE-VVA1 or placebo) will be considered as the baseline observation.

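### The pooled ANCOVA leaves out the factor used to stratify randomisation (hysterectomy history), so its P values may be somewhat too large; adding it costs one degree of freedom

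*Combined protocol and SAP*

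**What the plan says.** Section 9.5 says that participants "will be randomly assigned in a 1:1:1:1:1 ratio, by history of hysterectomy, to 1 of the 5 treatment groups", by permuted blocks. Section 7.1 gives the target: "such that each treatment group ends up with 4 hysterectomized women and 4 non-hysterectomized women, for a total of 8 women".

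The ANCOVA of change from baseline is described three times, each time with baseline score as the only covariate named:

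- Section 13.1.6.2: "vaginal pH, vaginal cytology, dyspareunia, and most bothersome symptom, using baseline score as a covariate".
- Section 13.1: the same outcomes, "using baseline score as a covariate. With no formal testing planned for this study".
- Synopsis: "vaginal pH, vaginal cytology, and most bothersome symptom, using baseline score as a covariate". Dyspareunia is missing from this list.

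Section 13.1.1 asks for every analysis in hysterectomised women, in non-hysterectomised women and in both together, so the pooled ANCOVA is a planned analysis. Section 13.1 calls itself a summary and adds: "An SAP that describes the details of the analyses to be conducted will be written prior to database lock". That SAP is not among the documents.

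**The concern.** A model that ignores a balanced stratification factor describes a less precise design than the one that was run. Stratified allocation removes the factor from the treatment contrast. If the factor is left out of the model, any effect it has on change beyond baseline is counted as residual noise. The model-based standard error, and the P value computed from it, then overstate the uncertainty of the dose-placebo difference.

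Little is at stake, because the P values carry no decision and the descriptive means and SDs by arm are unaffected. Even so, Section 13.2 says the study is meant to guide later designs, and a P value that is reported should match the design that produced it.

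**Working it through.** **Inputs from the document.** 5 arms of 8 give 5 × 8 = 40 women, and 5 × 4 = 20 per stratum, which agrees with Sections 7.1 and 13.2. There is no power calculation, alpha, SD or effect size to reproduce.

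**Assumptions (not in the document).** Stratum effect b = 0 to 1.0 residual SD after baseline adjustment; baseline slope −0.5; normal residuals with SD 1; stratum unrelated to baseline; exact 4+4 balance; two-sided 5% as a yardstick only.

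**Closed form.** Residual df are 40 − 5 − 1 = 34 without the stratum and 33 with it. Omitting a balanced yes/no factor adds 40 × 0.25 × b² = 10b² to the expected residual sum of squares. The reported SE is therefore too wide by a factor of about √(1 + 10b²/34):

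- b = 0.25: √(1 + 0.625/34) = 1.009
- b = 0.5: √(1 + 2.5/34) = 1.036
- b = 1.0: √(1 + 10/34) = 1.138

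**Simulation.** 20,000 null trials per setting, 20 mg versus placebo, ordinary least squares. Each pair is without / with the stratum; ratios were taken before rounding.

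| b | Mean reported SE | Ratio | Actual SE of estimate | Null rejection at 5% | Trials where the adjusted P is larger |
|---|---|---|---|---|---|
| 0 | 0.504 / 0.504 | 1.000 | 0.506 / 0.506 | 4.9% / 4.8% | 64% |
| 0.25 | 0.508 / 0.503 | 1.009 | 0.510 / 0.510 | 5.0% / 5.2% | 56% |
| 0.5 | 0.521 / 0.503 | 1.036 | 0.507 / 0.507 | 4.2% / 5.0% | 39% |
| 1.0 | 0.572 / 0.504 | 1.133 | 0.510 / 0.509 | 2.7% / 4.9% | 18% |

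The Monte Carlo error of a 5% rate is √(0.05 × 0.95 / 20,000) = 0.15 percentage points. The actual SE is the same under both models; only the reported one differs. The last column shows that the P value shift holds on average, not in every trial.

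**Second simulation** (12,000 trials per setting; ratio = reported SE / actual SE). At b = 0, 0.5 and 1.0, without the stratum:

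- The ratio is 0.996, 1.041 and 1.127, and the mean null P value is 0.499, 0.511 and 0.536, where 0.50 is correct.
- With an assumed true difference of 1.5 residual SD, power is 81.8, 80.4 and 73.7%, against about 82% with the stratum.
- If the stratum is *not* balanced by design (b = 1.0), the ratio is 0.988 and null rejection 5.4%. The excess therefore comes from omitting a factor that the design balances.

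**Sensitivity of the inflation at b = 0.5 and 1.0:**

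- Baseline differing by 1 SD between strata: about 2% and 10%.
- Four-level outcomes, as for the symptoms rated "as either not present (none), mild, moderate, or severe, and will indicate whether vaginal bleeding associated with vaginal activity is present or absent": about 3% and 11%.
- Strata of 23/17 or 28/12 (blocks of 5 assumed; block size is not stated): about 3% and 11–13%.
- 10% random dropout (b = 1.0 only): reported / actual SE 1.115, null rejection 2.8%.

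**If balance is lost.** Section 8.5 says "Participants who are withdrawn prior to completing all study visits may be replaced". As an illustration only, take placebo at 5+3 and 20 mg at 3+5. The unadjusted estimate shifts by (5/8 − 3/8)b = 0.25b in size in that data set (simulated means 0.127 and 0.256 at b = 0.5 and 1.0). Null rejection is 5.2% and 4.5%. With the stratum in the model the shift disappears (mean −0.002 and −0.006).

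**The case against.** The best case against is that Section 13 is a summary. It calls baseline score a covariate without saying it is the only one, and the SAP may add the stratum. Nothing in the document shows that hysterectomy status predicts change in pH, cytology or symptoms; women are separated mainly for endometrial safety, eligibility and confirmation of menopausal status. At b of 0.25 or less the inflation is at most 1%. No standard errors or confidence intervals are listed as outputs, so only informational P values are certainly affected. The estimates and descriptive SDs that would inform a later trial do not change. The within-stratum analyses are free of the problem.

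Much of this stands. The size is unknown and may be zero, the conservative direction depends on balance, and no passage says that a replacement would come from the other stratum.

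Three things do not follow:

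- Section 13.1.6.2 leaves further exposure-response detail to the SAP, and Section 13.1.6.3 does the same for the usability analysis. The ANCOVA covariates carry no such note, and a SAP that followed the wording would repeat the omission.
- The within-stratum models, with 20 − 5 − 1 = 14 residual df each, do not correct the pooled P value.
- An unknown stratum effect does not favour leaving the term out, because including it costs almost nothing if the effect is zero.

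**Conclusion.** The concern holds, as a minor one. The pooled ANCOVA as written does not reflect the stratified randomisation. If hysterectomy status predicts change beyond baseline, the model-based SEs and P values for dose-placebo differences are too large on average. The excess in the SE is about 4% at a stratum effect of 0.5 residual SD and 13% at 1.0, and nil if there is no effect. These sizes rest on assumed effects, normal outcomes and 4+4 balance. The estimates stay unbiased under that balance, their true precision is essentially unchanged, and no planned conclusion depends on the P values.

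**What to change.** In the synopsis, Section 13.1, Section 13.1.6.2 and the SAP, state the all-participants model as: change = treatment (5 levels) + baseline score + hysterectomy status (yes/no). The within-stratum ANCOVAs stay as they are. The same edit can bring the synopsis list of outcomes into line with Sections 13.1 and 13.1.6.2 on dyspareunia.

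The cost is one residual degree of freedom (34 to 33; critical t 2.032 to 2.035) and a wording change. The factor is already collected and used for randomisation.
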